14.3 Safety Data

14.3.1 Displays of Adverse Events

Table 51: Overall Summary of Adverse Events

	4CMenB (N = x)		Placebo (N = x)		All Participants (N = x)	
Participants ^a with	n	%	n	%	n	%
At least one solicited adverse event						
At least one local solicited adverse event	x	x	x	x	x	x
At least one systemic solicited adverse event	x	x	x	x	x	x
At least one solicited adverse event due to rectal mucosal biopsy procedure	x	x	x	x	x	x
At least one unsolicited adverse event	x	x	x	x	x	x
Mild (Grade 1)	x	x	x	x	x	x
Moderate (Grade 2)	x	x	x	x	x	x
Severe (Grade 3)	x	x	x	x	x	x
Not yet assessed	x	x	x	x	x	x
At least one related unsolicited adverse event	x	x	x	x	x	x
Mild (Grade 1)	x	x	x	x	x	x
Moderate (Grade 2)	x	x	x	x	x	x
Severe (Grade 3)	x	x	x	x	x	x
Not yet assessed	x	x	x	x	x	x
At least one severe (Grade 3) unsolicited adverse event	x	x	x	x	x	x
Related	x	x	x	x	x	x
Unrelated	x	x	x	x	x	x
At least one serious adverse event ^b	x	x	x	x	x	x
At least one related, serious adverse event	x	x	x	x	x	x
At least one adverse event leading to early termination ^c	x	x	x	x	x	x
At least one medically attended adverse event	x	x	x	x	x	x

Note: N = Number of participants in the Safety Population

^a Participants are counted once for each category regardless of the number of events.

^b A listing of Serious Adverse Events is included in Section 9.3

^c As reported on the Adverse Event eCRF.

14.3.2 Listing of Deaths, Other Serious and Significant Adverse Events

Table 52: Listing of Serious Adverse Events– Safety Population

[Implementation Note: This listing is included in the table shells document, as it is included in the body of the CSR. If the event is ongoing (no stop date), indicate “ongoing” for the “Duration”. If more than one reason is selected for the reason reported as an SAE, list all reasons in the column, separated by a comma. In the “If Not Related, Alternate Etiology” column, merge the 2 data fields for collecting alternate etiology, separate by a colon. If there are no comments for an event, populate ‘Comments’ row with ‘None’. Add columns for MedDRA HLT or LLT depending on halting criteria or other study needs. In the CSR, Participant ID should be USUBJID (not PATID) for purposes of de-identification. Listing should be sorted by Treatment Group, Participant ID, Associated with Dose No., and No. of Days Post Associated Dose.]

Adverse Event	Associated with Dose No.	No. of Days Post Associated Dose (Duration)	No. of Days Post Dose the Event Became Serious	Reason Reported as an SAE	Severity	Relationship to Study Treatment	If Not Related, Alternative Etiology	Action Taken with Study Treatment	Participant Discontinued Due to AE	Outcome	MedDRA System Organ Class	MedDRA Preferred Term
Treatment Group: , Participant ID: , AE Number:												
Comments:												
Participant ID: , Treatment Group: , AE Number:												
Comments:												

Table 53: Listing of Non-Serious Adverse Events of Moderate or Greater Severity – Safety Population

[Implementation Note: Listing should be sorted by Treatment Group, Participant ID, Associated with Dose No., and No. of Days Post Associated Dose.]

Adverse Event	Associated with Dose No.	No. of Days Post Associated Dose (Duration)	No. of Days Post Dose the Event Became Serious	Severity	Relationship to Study Treatment	If Not Related, Alternative Etiology	Action Taken with Study Treatment	Participant Discontinued Due to AE	Outcome	MedDRA System Organ Class	MedDRA Preferred Term
Treatment Group: , Participant ID: , AE Number:											
Comments:											
Participant ID: , Treatment Group: , AE Number:											
Comments:											

Table 54: Adverse Events Occurring in $\geq 5\%$ of Participants in Any Treatment Group by MedDRA System Organ Class and Preferred Term, and Treatment Group - Safety Population

Preferred Term	MedDRA System Organ Class	4CMenB (N=X)			Placebo (N=X)			All Participants (N=X)		
		n	%	Events	n	%	Events	n	%	Events
Serious Adverse Events										
All	All	x	x	x	x	x	x	x	x	x
PT1	SOC1	x	x	x	x	x	x	x	x	x
Etc.	Etc.	x	x	x	x	x	x	x	x	x
Other (Non-serious) Adverse Events										
All	All	x	x	x	x	x	x	x	x	x
PT1	SOC1	x	x	x	x	x	x	x	x	x
Etc.	Etc.	x	x	x	x	x	x	x	x	x

Notes: N = number of participants in the Safety Population (number of participants at risk).

n= number of participants reporting event.

Events= total frequency of events reported.

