10.5.4 Safety Analysis Plan

Safety evaluations will be based on the frequency and severity of reactogenicity events, AEs, and SAEs occurring from the time of first study product administration through the final study visit.

AEs and SAEs will be coded by Medical Dictionary for Regulatory Activities (MedDRA®) for preferred term and system organ class. The rate and exact 95% CIs of AEs and SAEs in aggregate, as well as by MedDRA categories, will be computed. The number of SAEs will be reported by a detailed listing showing the type, MedDRA coding, relevant dates (treatment dosing date(s) and SAE onset and resolution dates), severity, relatedness, and outcome for each event.

Solicited local injection site and systemic reactogenicity will be summarized by severity for each day post injection (for each injection) and as the maximum severity over the entire assessment period (across injections). Additionally, solicited AEs will be analyzed by taking the most severe response over the follow-up period, dichotomizing into a binary variable (none vs. any severity) and using exact confidence intervals to summarize the proportion/percentage of subjects reporting each symptom any infection site symptom, and any systemic symptom. Solicited AEs will be summarized separately for each infection, and over both injections by study arm.

Vital sign and physical exam findings will also be summarized and/or provided in subject-level listings.

Missing safety data will not be imputed and no search for outliers will be performed.

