3.2.2. Secondary Outcomes

- Serum IgG concentrations (GMT) against GC OMV antigens at Day 1, 29, 43, 57, and 181 in each treatment group
- Frequency and severity of any AE related to 4CMenB immunization through the end of the study.
- Frequency of SAEs through the end of the study.

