9.3. Adverse Events

Unsolicited AEs and SAEs will be coded by MedDRA for preferred term (PT) and system organ class (SOC). AEs will also be graded for severity. For each AE experienced, the participant will be asked if he/she had received medical attention, defined as hospitalization, an ER visit, or an otherwise unscheduled visit to or from medical personnel for any reason. AEs characterized by such unscheduled medical care will be designated as MAAEs. Safety will be assessed by the frequency and severity of:

- Any AE related to 4CMenB immunization through the end of the study.
- Any AE related to rectal mucosal sampling procedures through the end of the study.
- Any SAEs through the end of the study

A summary of all adverse events is provided in **Table 51**. This information is also presented graphically in **Figure 88** with number and severity of AEs categorized by MedDRA System Organ Class and treatment group. A summary of those events that occurred in $\geq 5\%$ of participants in any treatment group is provided in **Table 54**.

9.3.1. **Solicited Events and Symptoms**

Systemic solicited adverse events were collected pre-vaccination, and systemic and local solicited adverse events were collected 30 minutes post-vaccination and then daily for 7 days after each vaccination and graded on a severity scale of 0 (absent), 1 (mild), 2 (moderate) and 3 (severe). Systemic events include fever, chills/shivering/sweating, fatigue, malaise, myalgia and arthralgia (exclusive of the injection site), headache, and nausea. Local events include pain at injection site, pruritus, erythema, ecchymosis, induration/swelling, pain, and tenderness. **Table 56** summarizes the solicited adverse event grading scale.

The proportion of participants reporting at least one solicited adverse event will be summarized for each solicited adverse event, any systemic symptom, any local symptom, and any symptoms. The 95% CI will be calculated using Clopper-Pearson methodology from a binomial distribution (**Table 55**).

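### SAP Table 54 applies its 5% cutoff to the SAE block, so at 40/10 a lone placebo SAE gets a term row and a lone 4CMenB SAE usually does not; and no output gives an SAE-only rate with the exact CI the protocol commits to

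*SAP*

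**What the plan says.** **The cutoff.** SAP 9.3 introduces the table with "A summary of those events that occurred in $\geq 5\%$ of participants in any treatment group is provided in" Table 54, and the shell title repeats the rule: "Table 54: Adverse Events Occurring in $\geq 5\%$ of Participants in Any Treatment Group by MedDRA System Organ Class and Preferred Term". The body has two blocks, "Serious Adverse Events" and "Other (Non-serious) Adverse Events", each with an All row and preferred-term rows. The columns are n, % and events, and the denominator is the Safety Population of each arm. Neither SAP 9.3 nor the shell exempts the serious block.

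**The endpoint and its interval.** SAP 3.2.2 lists as a secondary outcome: "Frequency of SAEs through the end of the study". Protocol 10.5.4 states: "The rate and exact 95% CIs of AEs and SAEs in aggregate, as well as by MedDRA categories, will be computed". SAP 6.1 adds that safety variables get exact binomial intervals.

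**Where SAEs appear.**
- Table 51 has the row "At least one serious adverse event" and a row for related SAEs, with n and % only.
- Table 52 lists SAEs with system organ class and preferred term.
- Listing 25 lists all unsolicited AEs with an SAE flag.
- Table 61 has a CI column, but SAP 9.3.2 defines it for unsolicited AEs with serious and non-serious events combined.

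**The concern.** A frequency cutoff is a normal way to keep a table of common events short. Applied to serious events it works against the table's purpose, since SAEs in a trial this small are expected to be isolated. With 4:1 allocation it also treats the arms differently: a single participant always clears 5% in the small placebo arm and never does in the larger vaccine arm. A reader who takes the Table 54 serious block as the SAE summary could see a placebo SAE and no vaccine SAE when one occurred in each arm.

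The missing interval is a separate matter. SAE frequency is a secondary endpoint, and the likeliest result is zero or one event per arm. A bare 0% in both arms gives no indication of how little 40 and 10 participants can rule out.

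**Working it through.** **Inputs.** Planned arms are 40 and 10 (SAP 5). Allocation is 4:1 with about 50 and at most 60 enrolled (protocol 10.2). The cutoff is 5% in any treatment group (SAP 9.3, Table 54 title).

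**Arm sizes reproduced.** 50 × 4/5 = 40 and 50 × 1/5 = 10, as planned. At the maximum, 60 × 4/5 = 48 and 60 × 1/5 = 12.

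**Cutoff by arm.** One participant contributes 1/N. The fewest participants with the same preferred term that reach 5% is 0.05 × N rounded up. The two smaller splits are the reduced sample sizes in protocol Table 2.

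| 4CMenB / placebo | 1/N, 4CMenB | 1/N, placebo | Needed, 4CMenB | Needed, placebo |
|---|---|---|---|---|
| 30 / 6 | 3.3% | 16.7% | 2 | 1 |
| 35 / 8 | 2.9% | 12.5% | 2 | 1 |
| 40 / 10 | 2.5% | 10.0% | 2 | 1 |
| 48 / 12 | 2.1% | 8.3% | 3 | 1 |

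Any placebo arm of 20 or fewer shows every single event (1/20 = 5%). On unrounded percentages the 4CMenB arm needs 3 from N = 41, because 2/41 = 4.88%. SAP 11 prints percentages as whole numbers, so 2/41 would print as 5%, and the SAP does not say which value governs. This does not affect the 40/10 result, since 2.5% is below 5% either way.

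**Exact intervals.** Clopper-Pearson limits for x of n are the 2.5% quantile of Beta(x, n − x + 1) and the 97.5% quantile of Beta(x + 1, n − x), with a lower limit of 0 when x = 0. For x = 0 the upper limit reduces to 1 − 0.025^(1/n).

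| x/n | Rate | Exact 95% CI |
|---|---|---|
| 0/40 | 0% | 0 to 8.8% |
| 1/40 | 2.5% | 0.1 to 13.2% |
| 0/10 | 0% | 0 to 30.8% |
| 1/10 | 10% | 0.3 to 44.5% |

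**How likely an isolated case is.** Protocol 2.3.1 cites 54 individuals with an SAE among 16,974 vaccinated, or 0.32%. If that rate applied here, the chance of at least one affected participant among 40 is 1 − (1 − 0.00318)^40 = 12.0%. The chance of exactly one is 40 × 0.00318 × (1 − 0.00318)^39 = 11.2%. So when any 4CMenB participant is affected, it is exactly one in 11.2/12.0, about 94%, of cases. That describes how many participants are affected. It is not the probability that a term row is omitted, which also depends on shared terms and on the placebo arm.

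**The case against.** A reader might infer that vaccine-arm SAEs are dropped from the report. The documents do not support that. Table 51 counts participants with any SAE and with any related SAE in each arm without a cutoff, so the endpoint frequency is reported in full. Table 52 lists SAEs by treatment group with system organ class and preferred term, and its implementation note puts it in the body of the study report. Listing 25 flags each SAE. Tables 61 and 62 count serious events by term without a cutoff, mixed with non-serious ones. With few SAEs expected, Table 52 gives a careful reader almost everything a by-term table could. All of this stands, and it limits the point to the Table 54 display.

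Two details limit it further. The cutoff works per preferred term and in any arm, so a 4CMenB SAE is shown if its term reaches 5% in placebo. The shell also leaves open whether the block's All row is filtered. If it is not, Table 54 still counts a lone 4CMenB SAE there, without a matching row beneath. If it is, the row could show zero while Table 51 shows one.

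A reader might also infer that the SAP has given up exact intervals for safety. It has not: SAP 6.1 keeps the commitment and Table 61 has a CI column. One could read the protocol sentence as covering AEs and SAEs pooled, which Table 61 would satisfy. That reading is possible but strained, because SAEs are already AEs and would not need separate mention. The following sentence of protocol 10.5.4 asks for a detailed SAE listing, which adds to the interval commitment and does not replace it. Finally, anyone can compute the interval from n and N, and no hypothesis test depends on it. That is true, but the protocol says it will be computed and SAP 13 declares no departure.

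**Conclusion.** The concern holds in two limited parts. First, the cutoff as written covers the SAE block. At 40/10 a lone 4CMenB SAE term (2.5%) is omitted unless placebo reaches 5% on the same term, while a lone placebo SAE term (10%) is always shown. The asymmetry persists at all four splits checked. It affects the only SAE-specific count table by MedDRA term, not the presence of SAEs in the report or the Table 51 endpoint count. Second, no shell isolates the SAE rate with an exact interval, in aggregate or by MedDRA category, on the natural reading of protocol 10.5.4.

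The arithmetic assumes Safety Populations near the planned arm sizes and a cutoff applied literally to each preferred-term row. The 12.0% figure also assumes that the cited campaign rate carries over to this trial. This is a reporting defect that should be corrected in the shells; it changes no data or estimate.

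**What to change.** 1. In SAP 9.3 and the Table 54 title, state that the 5% cutoff applies only to the non-serious block and that every SAE preferred term is listed whatever its frequency.
2. Add a note that the All row of the SAE block counts all participants with an SAE, so that it agrees with Table 51.
3. Add Clopper-Pearson 95% intervals by arm to the two SAE rows of Table 51 and to each row of the Table 54 SAE block. SAP 9.3.1 already specifies this method for solicited events in Table 55.
4. State whether the cutoff for non-serious events uses unrounded percentages.

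The cost is a few sentences of SAP text and a CI column in the shells. It needs no new data, assay or visit.

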14.3.1.1 Solicited Adverse Events

Table 55: Number and Percentage of Participants Experiencing Solicited Events with 95% Confidence Intervals by Symptom, Maximum Severity, Dose, and Treatment Group – Safety Population

Symptom	Severity	Post Dose 1 - 4CMenB (N=X)			Post Dose 1 - Placebo (N=X)			Post Dose 2 - 4CMenB (N=X)			Post Dose 2 - Placebo (N=X)			Post Either Dose-4CMenB (N=X)			Post Either Dose Placebo (N=X)		
		n	%	95% CI ^a	n	%	95% CI ^a	n	%	95% CI ^a	n	%	95% CI ^a	n	%	95% CI ^a	n	%	95% CI ^a
Any Symptom	Any Severity	x	xx	x, x	x	xx	x, x	x	xx	x, x	x	xx	x, x	x	xx	x, x	x	xx	x, x
	None	x	xx	x, x	x	xx	x, x	x	xx	x, x	x	xx	x, x	x	xx	x, x	x	xx	x, x
	Mild	x	xx	x, x	x	xx	x, x	x	xx	x, x	x	xx	x, x	x	xx	x, x	x	xx	x, x
	Moderate	x	xx	x, x	x	xx	x, x	x	xx	x, x	x	xx	x, x	x	xx	x, x	x	xx	x, x
	Severe	x	xx	x, x	x	xx	x, x	x	xx	x, x	x	xx	x, x	x	xx	x, x	x	xx	x, x
Systemic Symptoms																			
Any Systemic Symptom	Any Severity	x	xx	x, x	x	xx	x, x	x	xx	x, x	x	xx	x, x	x	xx	x, x	x	xx	x, x
	None	x	xx	x, x	x	xx	x, x	x	xx	x, x	x	xx	x, x	x	xx	x, x	x	xx	x, x
	Mild	x	xx	x, x	x	xx	x, x	x	xx	x, x	x	xx	x, x	x	xx	x, x	x	xx	x, x
	Moderate	x	xx	x, x	x	xx	x, x	x	xx	x, x	x	xx	x, x	x	xx	x, x	x	xx	x, x
	Severe	x	xx	x, x	x	xx	x, x	x	xx	x, x	x	xx	x, x	x	xx	x, x	x	xx	x, x
[Systemic Symptom 1]	Any Severity	x	xx	x, x	x	xx	x, x	x	xx	x, x	x	xx	x, x	x	xx	x, x	x	xx	x, x
	None	x	xx	x, x	x	xx	x, x	x	xx	x, x	x	xx	x, x	x	xx	x, x	x	xx	x, x
	Mild	x	xx	x, x	x	xx	x, x	x	xx	x, x	x	xx	x, x	x	xx	x, x	x	xx	x, x
	Moderate	x	xx	x, x	x	xx	x, x	x	xx	x, x	x	xx	x, x	x	xx	x, x	x	xx	x, x
	Severe	x	xx	x, x	x	xx	x, x	x	xx	x, x	x	xx	x, x	x	xx	x, x	x	xx	x, x
[Systemic Symptom 2]	Any Severity	x	xx	x, x	x	xx	x, x	x	xx	x, x	x	xx	x, x	x	xx	x, x	x	xx	x, x
	None	x	xx	x, x	x	xx	x, x	x	xx	x, x	x	xx	x, x	x	xx	x, x	x	xx	x, x
	Mild	x	xx	x, x	x	xx	x, x	x	xx	x, x	x	xx	x, x	x	xx	x, x	x	xx	x, x
	Moderate	x	xx	x, x	x	xx	x, x	x	xx	x, x	x	xx	x, x	x	xx	x, x	x	xx	x, x
	Severe	x	xx	x, x	x	xx	x, x	x	xx	x, x	x	xx	x, x	x	xx	x, x	x	xx	x, x

Table 55: Number and Percentage of Participants Experiencing Solicited Events with 95% Confidence Intervals by Symptom, Maximum Severity, Dose, and Treatment Group – Safety Population (continued)

Symptom	Severity	Post Dose 1 - 4CMenB (N=X)			Post Dose 1 - Placebo (N=X)			Post Dose 2 - 4CMenB (N=X)			Post Dose 2 - Placebo (N=X)			Post Either Dose-4CMenB (N=X)			Post Either Dose Placebo (N=X)		
		n	%	95% CI ^a	n	%	95% CI ^a	n	%	95% CI ^a	n	%	95% CI ^a	n	%	95% CI ^a	n	%	95% CI ^a
Local Symptoms																			
Any Local Symptom	Any Severity	x	xx	x, x	x	xx	x, x	x	xx	x, x	x	xx	x, x	x	xx	x, x	x	xx	x, x
	None	x	xx	x, x	x	xx	x, x	x	xx	x, x	x	xx	x, x	x	xx	x, x	x	xx	x, x
	Mild	x	xx	x, x	x	xx	x, x	x	xx	x, x	x	xx	x, x	x	xx	x, x	x	xx	x, x
	Moderate	x	xx	x, x	x	xx	x, x	x	xx	x, x	x	xx	x, x	x	xx	x, x	x	xx	x, x
	Severe	x	xx	x, x	x	xx	x, x	x	xx	x, x	x	xx	x, x	x	xx	x, x	x	xx	x, x
[Local Symptom 1]	Any Severity	x	xx	x, x	x	xx	x, x	x	xx	x, x	x	xx	x, x	x	xx	x, x	x	xx	x, x
	None	x	xx	x, x	x	xx	x, x	x	xx	x, x	x	xx	x, x	x	xx	x, x	x	xx	x, x
	Mild	x	xx	x, x	x	xx	x, x	x	xx	x, x	x	xx	x, x	x	xx	x, x	x	xx	x, x
	Moderate	x	xx	x, x	x	xx	x, x	x	xx	x, x	x	xx	x, x	x	xx	x, x	x	xx	x, x
	Severe	x	xx	x, x	x	xx	x, x	x	xx	x, x	x	xx	x, x	x	xx	x, x	x	xx	x, x
[Local Symptom 2]	Any Severity	x	xx	x, x	x	xx	x, x	x	xx	x, x	x	xx	x, x	x	xx	x, x	x	xx	x, x
	None	x	xx	x, x	x	xx	x, x	x	xx	x, x	x	xx	x, x	x	xx	x, x	x	xx	x, x
	Mild	x	xx	x, x	x	xx	x, x	x	xx	x, x	x	xx	x, x	x	xx	x, x	x	xx	x, x
	Moderate	x	xx	x, x	x	xx	x, x	x	xx	x, x	x	xx	x, x	x	xx	x, x	x	xx	x, x
	Severe	x	xx	x, x	x	xx	x, x	x	xx	x, x	x	xx	x, x	x	xx	x, x	x	xx	x, x

Note: N = Number of participants in the Safety Population who received the specified dose. Severity is the maximum severity reported over all solicited symptoms post dosing for each participant.

^a The 95% CI of the proportion will be calculated using Clopper-Pearson (Exact) methodology from a binomial distribution.

Table 56: Number and Percentage of Participants Experiencing Solicited Events by Symptom, Severity, and Day Post Dosing - 4CMenB, Post Dose 1

Symptom	Severity	Pre-Dose 1		Post-Dose 1		Day 1		Day 2		Day 3		Day 4		Day 5		Day 6		Day 7+	
		n	%	n	%	n	%	n	%	n	%	n	%	n	%	n	%	n	%
Any Symptom	None	x	xx	x	xx	x	xx	x	xx	x	xx	x	xx	x	xx	x	xx	x	xx
	Mild																		
	Moderate																		
	Severe																		
	Not Reported																		
Systemic Symptoms																			
Any Systemic Symptom	None	x	xx	x	xx	x	xx	X	xx	x	xx	x	xx	x	xx	x	xx	x	xx
	Mild																		
	Moderate																		
	Severe																		
	Not Reported																		
[Systemic Symptom 1]	None																		
	Mild																		
	Moderate																		
	Severe																		
	Not Reported																		
[Systemic Symptom 2]	None																		
	Mild																		
	Moderate																		
	Severe																		
	Not Reported																		
Local Symptoms																			
Any Local Symptom	None	x	xx	x	xx	x	xx	X	xx	x	xx	x	xx	x	xx	x	xx	x	xx
	Mild																		

Table 56: Number and Percentage of Participants Experiencing Solicited Events by Symptom, Severity, and Day Post Dosing - 4CMenB, Post Dose 1 (continued)

Symptom	Severity	Pre-Dose 1		Post-Dose 1		Day 1		Day 2		Day 3		Day 4		Day 5		Day 6		Day 7+	
		n	%	n	%	n	%	n	%	n	%	n	%	n	%	n	%	n	%
	Moderate																		
	Severe																		
	Not Reported																		
[Local Symptom 1]	None																		
	Mild																		
	Moderate																		
	Severe																		
	Not Reported																		
[Local Symptom 2]	None																		
	Mild																		
	Moderate																		
	Severe																		
	Not Reported																		

Note: N = Number of participants in the Safety Population who received the specified dose. Severity is the maximum severity reported post dosing for each participant for each day.

Tables with similar format:

Table 57: Number and Percentage of Participants Experiencing Solicited Events by Symptom, Severity, and Day Post Dosing- 4CMenB, Post Dose 2

Table 58: Number and Percentage of Participants Experiencing Solicited Events by Symptom, Severity, and Day Post Dosing- Placebo, Post Dose 1

Table 59: Number and Percentage of Participants Experiencing Solicited Events by Symptom, Severity, and Day - Placebo, Post Dose 2

Table 60: Number and Percentage of Participants Experiencing Solicited Events for Dose 1 Compared with Dose 2 by Treatment Group

Treatment Group		Dose 2 – Participants with No Symptoms	Dose 2 – Participants with Mild or Greater Symptoms	Dose 2 – Total Number of Participants
Systemic Symptoms				
4CMenB	Dose 1 Participant with No Symptoms	x (%)	x (%)	x (%)
	Dose 1 Participants with Mild or Greater Symptoms	x (%)	x (%)	x (%)
	Dose 1 Total Number of Participants	x (%)	x (%)	x (100%)
Placebo	Dose 1 Participant with No Symptoms	x (%)	x (%)	x (%)
	Dose 1 Participants with Mild or Greater Symptoms	x (%)	x (%)	x (%)
	Dose 1 Total Number of Participants	x (%)	x (%)	x (100%)
Local Symptoms				
4CMenB	Dose 1 Participants with No Symptoms	x (%)	x (%)	x (%)
	Dose 1 Participants with Mild or Greater Symptoms	x (%)	x (%)	x (%)
	Dose 1 Total Number of Participants	x (%)	x (%)	x (100%)
Placebo	Dose 1 Participants with No Symptoms	x (%)	x (%)	x (%)
	Dose 1 Participants with Mild or Greater Symptoms	x (%)	x (%)	x (%)
	Dose Total Number of Participants	x (%)	x (%)	x (100%)

Notes: Denominators for percentages are the number of participants in the Safety Population who received both the first and second dose.

[x] participants did not get the second dose and are not included in this table.

14.3.1.2 Unsolicited Adverse Events

Table 61: Summary of Unsolicited Adverse Events by MedDRA System Organ Class and Preferred Term, Dose Number, and Treatment Group

4CMenB													
MedDRA Preferred Term	MedDRA Preferred Term	Post Dose 1 (N=X)				Post Dose 2 (N=X)				Post Any Dose (N=X)			
		n	%	95% CI	Events	n	%	95% CI	Events	n	%	95% CI	Events
Any SOC	Any PT	x	xx	xx, xx	x	x	xx	xx, xx	x	x	xx	xx, xx	x
[SOC 1]	Any PT												
	[PT 1]												
	[PT 2]												
[SOC 2]	Any PT												
	[PT 1]												
	[PT 2]												
Placebo													
MedDRA System Organ Class	MedDRA Preferred Term	Post Dose 1 (N=X)				Post Dose 2 (N=X)				Post Any Dose (N=X)			
		n	%	95% CI	Events	n	%	95% CI	Events	n	%	95% CI	Events
Any SOC	Any PT	x	xx	xx, xx	x	x	xx	xx, xx	x	x	xx	xx, xx	x
[SOC 1]	Any PT												
	[PT 1]												
	[PT 2]												
[SOC 2]	Any PT												
	[PT 1]												
	[PT 2]												

Note: N = number of participants in the Safety Population who received the specified dose. This table presents number and percentage of participants. A participant is only counted once per PT/time point.

Table 62: Unsolicited Adverse Events by MedDRA System Organ Class and Preferred Term, Maximum Severity, Relationship, and Treatment Group

MedDRA System Organ Class	Preferred Term	Severity	4CMenB (N = X)						Placebo (N = X)						All Participants (N = X)					
			Related		Not Related		Total		Related		Not Related		Total		Related		Not Related		Total	
			n	%	n	%	n	%	n	%	n	%	n	%	n	%	n	%	n	%
Any SOC	Any PT	Any Severity	x	xx	x	xx	x	xx	x	xx	x	xx	x	xx	x	xx	x	xx	x	xx
		Mild	x	xx	x	xx	x	xx	x	xx	x	xx	x	xx	x	xx	x	xx	x	xx
		Moderate	x	xx	x	xx	x	xx	x	xx	x	xx	x	xx	x	xx	x	xx	x	xx
		Severe	x	xx	x	xx	x	xx	x	xx	x	xx	x	xx	x	xx	x	xx	x	xx
SOC 1	PT 1	Any Severity	x	xx	x	xx	x	xx	x	xx	x	xx	x	xx	x	xx	x	xx	x	xx
		Mild	x	xx	x	xx	x	xx	x	xx	x	xx	x	xx	x	xx	x	xx	x	xx
		Moderate	x	xx	x	xx	x	xx	x	xx	x	xx	x	xx	x	xx	x	xx	x	xx
		Severe	x	xx	x	xx	x	xx	x	xx	x	xx	x	xx	x	xx	x	xx	x	xx
	PT 2	Any Severity	x	xx	x	xx	x	xx	x	xx	x	xx	x	xx	x	xx	x	xx	x	xx
		Mild	x	xx	x	xx	x	xx	x	xx	x	xx	x	xx	x	xx	x	xx	x	xx
		Moderate	x	xx	x	xx	x	xx	x	xx	x	xx	x	xx	x	xx	x	xx	x	xx
		Severe	x	xx	x	xx	x	xx	x	xx	x	xx	x	xx	x	xx	x	xx	x	xx

Note: N = Number of participants in the Safety Population.

Table 63: Related Unsolicited Adverse Events Within 7 Days Post Dosing by MedDRA System Organ Class and Preferred Term, Dose, and Treatment Group

[Implementation Note: Day x-y interval should correspond to period of collection for solicited symptoms, if applicable.]

Treatment Group	MedDRA System Organ Class	MedDRA Preferred Term	Day 1-7 Post Dose 1			Day 1-7 Post Dose 2			Within 7 Days Post Either Dose		
			n	%	Events	n	%	Events	n	%	Events
4CMenB (N = X)	Any SOC	Any PT	x	xx	x	x	xx	x	x	xx	x
	[SOC 1]	Any PT									
		[PT 1]									
		[PT 2]									
	[SOC 2]	Any PT									
		[PT 1]									
		[PT 2]									
Placebo (N=X)	Any SOC	Any PT	x	xx	x	x	xx	x	x	xx	x
	[SOC 1]	Any PT									
		[PT 1]									
		[PT 2]									

Note: N = Number of participants in the Safety Population. This table presents number and percentage of participants. For each time point, a participant is only counted once per PT.

Table 64: Laboratory Assessment --RPR Results - Safety Population

Time Point	Treatment Group	N	Positive		Negative		Missing	
			n	%	n	%	n	%
Baseline	4CMenB	X	X	XX	X	XX	X	XX
	Placebo							
Day 29	4CMenB							
	Placebo							
Day 181	4CMenB							
	Placebo							
Max Severity Post Baseline	4CMenB							
	Placebo							

Note: N = Number of available participants in the Safety Population at certain time

Table of Figures (continued)

Table 65: Laboratory Assessment --HIV Antibody Testing Results - Safety Population

Time Point	Treatment Group	N	Positive		Negative		Missing	
			n	%	n	%	n	%
Baseline	4CMenB	x	x	xx	x	xx	x	xx
	Placebo							
Day 181	4CMenB							
	Placebo							
Max Severity Post Baseline	4CMenB							
	Placebo							

Note: N = Number of available participants in the Safety Population at certain time

Table of Figures (continued)

Table 66: Laboratory Assessment – Chlamydia NAAT Testing Results - Safety Population

Test	Time Point	Treatment Group	N	Positive		Negative		Missing	
				n	%	n	%	n	%
Chlamydia NAAT Genitourinary	Baseline	4CMenB	x	x	xx	x	xx	x	xx
		Placebo							
	Day 29	4CMenB							
		Placebo							
	Day 181	4CMenB							
		Placebo							
Chlamydia NAAT Rectal	Baseline	4CMenB							
		Placebo							
	Day 29	4CMenB							
		Placebo							
	Day 181	4CMenB							
		Placebo							
Chlamydia NAAT Pharyngeal	Baseline	4CMenB							
		Placebo							
	Day 29	4CMenB							
		Placebo							
	Day 181	4CMenB							
		Placebo							

Note: N = Number of available participants in the Safety Population at certain time

Table of Figures (continued)

Table 67: Laboratory Assessment – Gonorrhea NAAT Testing Results - Safety Population

Test	Time Point	Treatment Group	N	Positive		Negative		Missing	
				n	%	n	%	n	%
Gonorrhea NAAT Genitourinary	Baseline	4CMenB	x	x	xx	x	xx	x	xx
		Placebo							
	Day 29	4CMenB							
		Placebo							
	Day 181	4CMenB							
		Placebo							
Gonorrhea NAAT Rectal	Baseline	4CMenB							
		Placebo							
	Day 29	4CMenB							
		Placebo							
	Day 181	4CMenB							
		Placebo							
Gonorrhea NAAT Pharyngeal	Baseline	4CMenB							
		Placebo							
	Day 29	4CMenB							
		Placebo							
	Day 181	4CMenB							
		Placebo							

Note: N = Number of available participants in the Safety Population at certain time.

Table of Figures (continued)

Table 68: Laboratory Assessment – Trichomonas Testing Results - Safety Population

Time Point	Treatment Group	N	Positive		Negative		Missing	
			n	%	n	%	n	%
Baseline	4CMenB	x	x	xx	x	xx	x	xx
	Placebo							
Day 29	4CMenB							
	Placebo							
Day 181	4CMenB							
	Placebo							

Note: N = Number of available participants in the Safety Population at certain time.

Table 69: Number and Percentage of Participants with Prior and Concurrent Medications by WHO Drug Classification and Treatment Group

WHO Drug Code Level 1, Anatomic Group	WHO Drug Code Level 2, Therapeutic Subgroup	4CMenB (N=X)		Placebo (N=X)		All Participants (N=X)	
		n	%	n	%	n	%
Any Level 1 Codes	Any Level 2 Codes	x	xx	x	xx	x	xx
[ATC Level 1 - 1]	Any [ATC 1 - 1]						
	[ATC 2 - 1]						
	[ATC 2 - 2]						
	[ATC 2 - 3]						
[ATC Level 1 - 2]	Any [ATC 1 - 2]						
	[ATC 2 - 1]						
	[ATC 2 - 2]						

Note: N = Number of participants in each group in the Safety Population.

n = Number of participants reporting taking at least one medication in the specific WHO Drug Class.

